NCT03496610

- **Study Title:**

Intraoperative surgical wound infiltration vs Quadratus Lumborum (QL) Block for post-operative pain control after nephrectomy in living donor kidney transplant patients.

- **Short Title:**

Surgeon infiltration QL block comparison

- **Research Abstract:**

The purpose of this study is to determine whether there is a difference between surgical site infiltration of local anesthetic versus ultrasound-guided truncal block ( Quadratus Lumborum, QL block). Current practice at Duke is to infiltrate local anesthetic at the end of surgery by the surgical team or request a member of the regional anesthesia division to provide a QL block.

Given that the administration of a QL block utilizes ultrasound to target a specific anatomical plane where the nerves providing sensation to the abdominal wall travel, we hypothesize that this approach will provide superior analgesia and improved morbidity when compared to direct injection of local anesthetic to the wound site.

We will utilize patients undergoing living donor nephrectomies since these are heavily screened and understood to be in excellent health thus eliminating potential confounding variables. These patients will be followed for 7 days after surgery and data will be collected pertaining to their total opioid consumption, pain scores, GI complications, and ability to return to normal pre-surgery physical function levels.

Both parametric and non-parametric data will be analyzed with the appropriate statistical tests. Patients risks will be the same as for patients undergoing donor nephrectomy who are not participating in the study.

- **Primary Objectives:**

The purpose of this study is to determine whether there is a difference between surgical site infiltration of local anesthetic versus ultrasound-guided truncal block (Quadratus Lumborum, QL block). Specifically comparing total 24h opioid consumption.

- **Secondary Objectives:**

The exploratory objectives are:

- Pain scores at which other time points post surgery- hourly for the first four hours, at 6 hours, 12 hours, 24 hours, and 48 hours
- GI complications (bloating, nausea/vomiting, constipation)
- Total use of PRN pain medication for a total of 7 days post surgery.

- **Purpose of the Study:**

The purpose of this study is to determine whether there is a difference between surgical site infiltration of local anesthetic versus ultrasound-guided truncal block ( Quadratus Lumborum, QL block)

we hypothesize that this approach will provide superior analgesia and improved morbidity when compared to direct injection of local anesthetic to the wound site.

- **Background & Significance:**

In 2014 in the United States there were approximately 17,107 kidney transplants performed (<https://www.kidney.org/news/newsroom/factsheets/Organ-Donation-and-Transplantation-Stats>). Of these a portion, approximately 6,000, were from living donors. Currently there is no consensus on the perioperative pain management strategies for these patients. Given the recent national attention to the ongoing opioid epidemic it seems appropriate to develop non-opioid pain management alternatives. Such strategies have been shown to decrease hospital stay and reduce morbidity associated with opioid use such as nausea and vomiting. Use of local anesthetics during surgery is a strategy currently utilized to reduce opioid use. In this study we aim at answering the question of whether direct wound infiltration of local anesthetic by the surgeon in the field is as effective as U/S guided Quadratus Lumborum regional block.

The Quadraus Lumborum block was described by Blanco *et. Al.* as a way to provide analgesia to truncal/intraabdominal procedures. Relatively recent case reports and studies have shown it to be an effective post-operative analgesic option for abdominal surgery. Patients undergoing donor nephrectomies here at Duke Medical Center are already receiving liposomal bupivacaine infiltration by the surgeon or QL blocks with liposomal bupivacaine placed by members of the regional anesthesia team. This study will simply utilize the already existing infrastructure to formally investigate if one technique provides better pain control. We hypothesize the ultrasound guided QL block with liposomal bupivacaine will offer superior post-operative analgesia than surgical field wound infiltration, using decreased 24-h post operative opioid totals. Additionally, as secondary endpoints we will also be examining differences in numerical pain scores post-operatively, GI complications (bloating, nausea/vomiting, constipation) as well as improved functionality of basic motor activities such as walking.

Ultimately, we feel that those patients who stand to gain the most benefit from this new intervention will be the kidney transplant recipients. However, given that this population tends to have high co-morbidities, which may confound our findings, we have elected to initially carry out this study on living kidney donors. These patients undergo rigorous selection and are thus a population with low to no co-morbidities and in generally healthy state. Such a population would be ideal to elucidate differences between pain control strategies where the impact of confounding variables would be minimized.

In summary we believe this study will help develop an important strategy aimed at post-operative pain control. Additionally, this study will help the continued development of non-opioid alternatives to pain control and therefore reduce the overall opioid exposure of these patients during the perioperative period.

1. 271: Tap block under ultrasound guidance: the description of a 'no pops' technique. *Regional Anesthesia and Pain Medicine* 32, 130–130 (2007).

3. Kadam, V. R. Ultrasound-guided quadratus lumborum block as a postoperative analgesic technique for laparotomy. *J Anaesthesiol Clin Pharmacol* 29, 550–552 (2013).
4. Öksüz, G. et al. Quadratus Lumborum Block Versus Transversus Abdominis Plane Block in Children Undergoing Low Abdominal Surgery: A Randomized Controlled Trial. *Regional Anesthesia and Pain Medicine* 42, 674–679 (2017).

- **Design & Procedures:**

Preoperatively, patients will be given standard of care premedication: 975mg acetaminophen, 600mg gabapentin, and 80 mg Aprepitant by mouth prior to surgery. These medications may be altered or not given depending on patient comorbidities or other extenuating factors such as allergy/intolerance. Prior to surgery the patients will be randomized to receive either surgical infiltration or QL block. This randomization will be done utilizing an online research randomizer (<https://www.randomizer.org/>).

Intraoperatively, patients will be given general anesthesia with endotracheal intubation which is the standard of care for these types of procedures. Induction will be achieved with propofol, lidocaine, fentanyl and a non-depolarizing neuromuscular blocking agent. Maintenance will be achieved with sevoflurane. A total of 100 mcg of fentanyl will be given during the case, 25mcg at induction and 75mcg in incremental doses throughout the case at the discretion of the attending anesthesiologist. A one-time IV bolus of 10mg IV dexamethasone (will not be given in diabetic patients) will be administered at the beginning of the procedure. After the completion of the surgery the patient will either receive 266 mg of liposomal bupivacaine mixed with 50 mg non-liposomal bupivacaine infiltrated into the wound by the surgeon or they will get bilateral ultrasound guided Quadratus Lumborum blocks by the anesthesia team. At the conclusion of the case, full neuromuscular reversal will be given, patient will be extubated, and taken to the post-operative care unit (PACU).

Post operatively patients will receive Tylenol 650 mg PO Q6h, Gabapentin 100 mg PO Q8h, and Toradol 15 mg IV Q8h (for a total of 3 doses). Additionally, patients will have post-operative orders for supplementary pain control that include 25mcg IV fentanyl for breakthrough pain, Tramadol 25 mg PO Q6h for pain score of 4-6/10, and Tramadol 50 mg PO Q6h for pain scores 7-10/10.

Upon arriving to the PACU patients will be assessed to determine their level of pain as well as nausea/vomiting. Subjects' verbal pain scores (NRS 11), opioid consumption, and GI complications will be recorded hourly for the first four hours, at 6 hours, 12 hours, 24 hours, and 36 hours post-surgical intervention. 24h opioid consumption (IV morphine equivalents) will be calculated. On post op day 1 patients will be asked to ambulate a short distance of 50ft and we will record pain levels using the numerical pain score reported during this activity. After leaving the hospital patients will be contacted via telephone daily until post op day 7 and will be asked the same questions they were asked during their hospital stay to asses opioid consumption, nausea/vomiting events, and GI complications.

- **Selection of Subjects:**

ASA 1-2 patients aged 18-75 years old undergoing living donor nephrectomy will be enrolled. Patients will be identified in conjunction with the transplant service and will be first contacted by telephone by the primary investigator to determine eligibility and interest. If patients are interested in participating, the study will again be explained on admission to hospital and written informed consent will be obtained the day of surgery prior to receiving any sedation.

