  - Volunteers that are illiterate, blind, or do not understand English will not be eligible for this study.
- Do you plan to obtain written consent for the conduct of research?

- Yes

- **Subject's Capacity to Give Legally Effective Consent:**

Patients who do not have the capacity to give legally effective consent will not be approached for participation in this study.

- **Study Interventions:**

After the completion of the surgery the patient will either receive 266 mg of liposomal bupivacaine mixed with 50 mg non-liposomal bupivacaine infiltrated into the wound by the surgeon or they will get bilateral ultrasound guided Quadratus Lumborum blocks by the anesthesia team. At the conclusion of the case, full neuromuscular reversal will be given, patient will be extubated, and taken to the post-operative care unit (PACU).

- **Risk/Benefit Assessment:**

Risks of this study includes the following:

- Risks of Bupivacaine Liposome Given as a Nerve Block:
  - Greater than or Equal to 10% (Common):
    - Nausea, fever, constipation
  - At Least 2% but Less than 10% (Uncommon):
    - Muscle twitching, taste disturbance, urinary retention, fatigue, headache, confusion, low blood pressure, high blood pressure, itching, sweating, rapid heart rate, anxiety, fall, temporary swelling, sensory loss, change in liver function tests, hiccups, respiratory depression, bruising
  - Less than 2% (Rare):
    - Arrhythmia, slow heart rate, impaired hearing, blurred vision, chills, skin infection, lung/respiratory infection, wound secretion, white blood cell count increase, joint pain and swelling, back pain, decreased mobility, muscle spasms, muscle weakness or pain, tingling, fainting, sedation, delirium, urinary incontinence, cough, difficulty breathing, blister, redness, rash, bruising, blood clots in extremities, decreased blood pressure when standing
- Risks of Bupivacaine Liposome Given Directly Into the Surgical Wound:
  - Greater than or Equal to 10% (Common):
    - Nausea, constipation, vomiting
  - At Least 2% but Less than 10% (Uncommon):
    - Fever, dizziness, temporary swelling, anemia, low blood pressure, itching, rapid heart rate, headache, insomnia, muscle spasms, back pain, tiredness
  - Less than 2% (Rare):

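### Patients are randomised before surgery with no stated masking and no rule on who learns the arm, although patient masking looks feasible and the primary opioid total depends partly on patient-reported pain

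*Combined protocol and SAP*

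**What the plan says.** Design & Procedures states: "Prior to surgery the patients will be randomized to receive either surgical infiltration or QL block". An online randomizer is named as the tool. Nothing says who receives the result, when it is passed on, or to whom.

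Both techniques are placed at the same point, after surgery is complete. Either the surgeon infiltrates the wound, "or they will get bilateral ultrasound guided Quadratus Lumborum blocks by the anesthesia team". The next step in the text, in both Design & Procedures and Study Interventions, is: "At the conclusion of the case, full neuromuscular reversal will be given, patient will be extubated". The patient is under general anaesthesia until then.

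Supplementary postoperative orders are "25mcg IV fentanyl for breakthrough pain, Tramadol 25 mg PO Q6h for pain score of 4-6/10", with a larger tramadol dose for scores of 7 to 10. Non-opioids are scheduled in both arms: "Post operatively patients will receive Tylenol 650 mg PO Q6h, Gabapentin 100 mg PO Q8h, and Toradol 15 mg IV Q8h". The outcome data are patient-reported in part: "verbal pain scores (NRS 11), opioid consumption, and GI complications will be recorded hourly for the first four hours". The 24-hour opioid total in IV morphine equivalents is then calculated and is the primary outcome.

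Background & Significance hypothesises that the block "will offer superior post-operative analgesia than surgical field wound infiltration, using decreased 24-h post operative opioid totals". The same section also asks, neutrally, whether infiltration is as effective as the block.

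Design & Procedures, Study Interventions, and Data Analysis and Statistical Considerations contain no statement on masking, and none that the trial is open-label. The word blind occurs only about eyesight, under Consent Process.

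**The concern.** Opioid use looks like an objective outcome, but here part of it is set by what the patient says. The reported score decides whether tramadol is 0, 25 or 50 mg at a given time, and fentanyl is tied to breakthrough pain without a numeric threshold. A patient who knows the arm may report a slightly different score, and staff who know it may use fentanyl slightly differently. Either would enter the primary outcome directly, and the reported score is itself a secondary outcome.

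Because randomisation comes before surgery and there is no disclosure rule, a patient could be told the arm before induction without departing from the plan. Once patients know, no analysis can recover what they would have reported otherwise.

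**Working it through.** **1. The plan's own figure.** Inputs from Data Analysis and Statistical Considerations: alpha 0.05 (taken as two-sided), power 0.8, difference in means 2, effect size 1.0, equal allocation, 40 completers from up to 50 enrolled.

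- Implied SD = 2 / 1.0 = 2, in a unit the plan does not state.
- A t-test with d = 1.0 needs 16.71 per arm. Dividing by 0.864, the minimum relative efficiency of the Mann-Whitney test, gives 19.3, so 20 per arm and 40 in total.
- 40 / (1 − 0.20) = 50.

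The stated size is reproduced. Masking does not change it.

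**2. Effect of an assumed bias.** The documents give no bias size, so 0.1, 0.2 and 0.3 SD are assumptions. With n = 20 per arm, df = 38 and a critical value of 2.024, the noncentrality parameter is b × √(n/2) = b × √10, where b is the net standardised difference.

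| Assumed bias | No true effect: noncentrality | Rejection | Planned effect, bias opposing: net d | Power |
|---|---|---|---|---|
| 0 | 0 | 5.0% | 1.0 | 86.9% |
| 0.1 SD | 0.316 | 6.1% | 0.9 | 79.2% |
| 0.2 SD | 0.632 | 9.5% | 0.8 | 69.3% |
| 0.3 SD | 0.949 | 15.2% | 0.7 | 57.8% |

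Simulated Mann-Whitney rejection with normal data and no true effect is close: 5.9%, 9.0% and 14.6% for the three biases. These results are in SD units, so they do not depend on the unit of the planned difference of 2.

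**3. How large a bias the tramadol bands could pass on.** From the plan: 0 mg below a score of 4, 25 mg for 4 to 6, 50 mg for 7 to 10, and dosing every 6 hours, hence four slots in 24 hours. Assumed: mean score 1, 2, 3, 4 or 5; between- and within-patient SD of 1.5/1.5, 2/1 or 1/1.5; scores rounded and limited to 0–10. That makes 15 scenarios, each with 8,000 simulated trials of 20 per arm and no true difference, tested by Mann-Whitney.

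| Reporting shift in one arm | Eligible slots dosed | Tramadol difference | In SD | Rejection |
|---|---|---|---|---|
| 0.25 point | all | 2–8 mg | 0.09–0.19 | 5–9% |
| 0.25 point | half | 1–4 mg | – | 5.5–6.7% |
| 0.5 point | all | 4–16 mg | 0.16–0.38 | 8–21% |
| 0.5 point | half | 2–8 mg | 0.14–0.25 | 7–12% |

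Fentanyl is not modelled. For tramadol alone, the factor that converts to IV morphine equivalents does not affect the rejection rate.

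**4. Feasibility.** The order in the text is general anaesthesia, surgery, technique, reversal, extubation. The patient does not witness the technique, so delivery need not reveal the arm. What can reveal it is being told, seeing puncture or dressing sites, and feeling block effects. The first two can be controlled; the third cannot.

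**The case against.** The strongest reply is that this is a comparison of two active techniques, both already routine at the site, and that an open-label comparison of routine care is a legitimate design. That stands: the plan could keep that design, but it would have to say so and give reasons.

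The plan also limits the room for bias. Fixed score bands restrict staff discretion over tramadol, non-opioids are scheduled in both arms, and the total of intraoperative fentanyl is fixed. This stands for staff discretion. It does not protect against a shift in the reported score itself, and postoperative fentanyl has no score threshold.

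Masking would be imperfect. Operators must know the arm, PACU and ward staff may know it, and the Risk/Benefit Assessment lists sensory loss for the nerve block but not for wound infiltration, so some patients may infer their arm. This stands too; it reduces the gain without removing it.

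Title and consent pages are not available, and a masking statement could be there. The design, intervention and analysis sections are available and are silent.

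A reader might infer more than the documents support:

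- *That the result will be biased towards the block.* Only the investigators' expectation is documented, alongside a neutral question. Bias could create a difference or hide one.
- *That the bias could be half an SD or more.* The tramadol model reaches at most 0.38 SD at the shifts tested, and 0.25 SD if half the eligible slots are dosed.
- *That unmasked investigators collect the scores.* The wording on the day-1 walk, "we will record pain levels using the numerical pain score reported during this activity", is ordinary protocol phrasing and does not identify the collector.
- *That patients could be selected into an arm.* That is a question of concealment before assignment, which is separate from this point.

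**Conclusion.** The point holds as a cheap improvement to the design. As written, nothing keeps the patient unaware of the arm, while the primary outcome depends partly on what the patient reports and the described sequence would allow the arm to be withheld.

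The size of any bias is not known from the documents. Under the assumed inputs, a bias of 0.1 to 0.3 SD raises false rejection from 5% to about 6–15%, or lowers t-test power from 87% to about 79–58% if it opposes the planned effect. A half-point reporting shift through the tramadol bands gives roughly 7–21%; a quarter-point shift has little effect (5–9%). These figures rest on 20 per arm, a two-sided 5% test, and assumed score distributions and dosed fractions. They show that modest shifts could matter at this sample size, not that such shifts will occur.

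**What to change.** Add to Design & Procedures:

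1. The allocation is disclosed only to those who deliver the technique, as late as practical.
2. The patient is not told the arm at least until the 24-hour primary outcome is complete, and preferably until the day-7 call, unless clinical care requires it.
3. The same skin sites are covered in both arms, including the bilateral block sites in patients who received infiltration.
4. A statement that operators, and possibly PACU and ward staff, are not masked, and that some patients may infer their arm from block effects. Report this as a limitation.

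If patient masking is judged impractical, declare the trial open-label and give the reasons.

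The cost is a short amendment, extra dressings, and minor logistics, including some block-team scheduling when disclosure is late. Masking will remain imperfect. The sample size, doses and clinical rules do not change.

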### Exclusion

Patients will be excluded from the study if they meet one or more of the following Criteria:

- 1) ASA 3 or 5
- 2) Diagnosis of chronic pain
- 3) Daily chronic opioid use (over 3 months of continuous opioid use).
- 4) Inability to communicate pain scores or need for analgesia.
- 5) Infection at the site of block placement
- 6) Age under 18 years old or greater than 75 years old
- 7) Pregnant women (as determined by standard of care day-of surgery urine bHCG)
- 8) Intolerance/allergy to local anesthetics
- 9) Weight <50 kg
- 10) Suspected or known addiction to or abuse of illicit drug(s), prescription medicine(s), or alcohol within the past 2 years.
- 11) Uncontrolled anxiety, schizophrenia, or other psychiatric disorder that, in the opinion of the investigator, may interfere with study assessments or compliance.
- 12) Current or historical evidence of any clinically significant disease or condition that, in the opinion of the investigator, may increase the risk of surgery or complicate the subject's postoperative course.

- **Subject Recruitment and Compensation:**

Only patients who are having living donor nephrectomies are eligible for this study. We will not bias any demographic groups in identifying patients eligible for this study. A total of up to 50 patients will be consented from Duke University Medical Center. Patients will not receive any additional compensation for enrollment in this study.

Recruitment will be facilitated by use of Duke "My Chart." A recruitment letter will be sent to potential subjects on behalf of their anesthesia provider informing them of the study with the research team's contact phone number and email address which includes an opt-out option. Research team members will follow up 1 week after MyChart letters/communication have been sent if there has been no response from potential candidates. Written consent will be collected at in-person visit before surgery.

- **Consent Process:**

- Who will conduct the consent process with prospective participants?
  - PI, sub-Is

- Who will provide consent or permission
  - Participant ONLY (No LAR or parent/legal guardian)
- How much time will the prospective participant have between being approached about participating in the study and needing to decide whether or not to participate?

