A total of up to 50 participants will be enrolled in the study in order to get 7-day follow up data from 40 participants. Participants will be randomized equally between Surgical Field Block and Regional Anesthesia groups based on sample size calculation for a non-parametric Mann-Whitney Test with  $a=0.05$ ,  $b=0.8$ , difference in means=2, and effect size of 1.0. The sample size required for a non-parametric test will provide greater than 80% power if the data meet requirements for a parametric t-test (<https://www.stat.ubc.ca/~rollin/stats/ssize/n2.html>).

- **Data & Safety Monitoring:**

In accordance with federal regulations the PI will monitor for, review, and promptly report to the IRB and appropriate institutional officials, all unanticipated problems involving risks to subjects or others

that occur in the course of a subject's participation in a research study (45 CFR 46.103(b)(5)(i) and 21 CFR 56.108(b)(1)), all AE reports will be reported per the DUHS IRB policies. PI will be monitoring all AEs and submitting reports to the IRB per DUHS IRB policy.

- **Privacy, Data Storage, & Confidentiality:**

- Explain how you will ensure that the subject's privacy will be protected:
  - Potential subjects and their families will be approached private rooms. Any guests not involved in the consent process will be asked to leave the room during any such communications unless the patient allows them to be present. Efforts to maintain subject confidentiality will include following Federal Privacy Regulations which provide safeguards for privacy, security and authorized access. Except when required by law, subjects will not be identified by name, social security number, address, telephone number, or any other direct personal identifier in study records disclosed outside of Duke University Health System (DUHS). Subjects will not be revealed in any reports or publications resulting from this study. For records disclosed outside of DUHS, subjects will be assigned a unique code number. The paper and electronic data will be stored as per the RDSP
- Describe how research data will be stored and secured to ensure confidentiality:
  - The research data will be collected and stored utilizing the RedCap database approved by Duke Health System. Only appropriate personnel involved in the study will be given access to the database.

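### Allocation relies on a web randomizer with no locked list, concealment, release rule or record of draws described, which leaves selection bias possible

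*Combined protocol and SAP*

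**What the plan says.** The allocation text is short. Design & Procedures states: "Prior to surgery the patients will be randomized to receive either surgical infiltration or QL block". It then names the tool: "This randomization will be done utilizing an online research randomizer", with a link to a website. Data Analysis and Statistical Considerations adds: "Participants will be randomized equally between Surgical Field Block and Regional Anesthesia groups".

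The steps before assignment are in investigators' hands:

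- Under Selection of Subjects, candidates are "first contacted by telephone by the primary investigator to determine eligibility and interest".
- Under Consent Process, the PI and sub-investigators take consent. Selection of Subjects says that "written informed consent will be obtained the day of surgery prior to receiving any sedation"; Consent Process also allows it earlier.
- Exclusion 11 covers psychiatric disorder that, "in the opinion of the investigator, may interfere with study assessments or compliance". Exclusion 12 covers any clinically significant condition that, "in the opinion of the investigator, may increase the risk of surgery or complicate the subject's postoperative course".

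The protocol does not say who operates the randomizer, whether it produces one list or one draw per patient, or who holds the output. It is also silent on block size, on whether assignment follows consent and final eligibility, and on whether draws are logged. REDCap is named only for collecting and storing data, and the department statisticians only for the analyses.

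**The concern.** Randomization protects the comparison only if nobody who decides on entry can foresee or change the next assignment. The stated method does not secure that. There are two possible routes, and which one is open depends on a detail that the protocol leaves out:

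- **One draw per patient.** Nothing can be foreseen, but an unwelcome draw could be repeated unless it is logged and final.
- **A list visible to the enrolling team.** Redrawing is not the issue, but a patient could be deferred, or excluded under criterion 11 or 12, once the next arm is known.

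Either route could make the arms differ in expected opioid need before treatment. Criterion 12 is broad: it reaches conditions expected to complicate the postoperative course. Randomization and consent can both fall on the day of surgery, and their order is not fixed. Masking after assignment could not repair such an imbalance, and none is described. Without a record of draws, no planned analysis could detect it.

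**Working it through.** **1. The plan's own figure.** The inputs under Data Analysis and Statistical Considerations are α = 0.05 (two-sided assumed), 80% power, a difference of 2 and an effect size of 1.0, so SD = 2/1.0 = 2. The t-test needs 16.7 per arm. Dividing by the worst-case Mann-Whitney efficiency of 0.864 gives 16.7/0.864 = 19.3, so 20 per arm and 40 in total. With 20% loss, 40/0.8 = 50. Both figures reproduce, and nothing below changes them.

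**2. An assumed steering mechanism.** None of these inputs is in the documents.

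- Expected opioid need E is standard normal and correlates r = 0.3–0.5 with the outcome.
- There is no treatment effect, and each donor is drawn 1:1.
- A donor in the top quarter of E who is drawn to QL is moved to infiltration with probability f.

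The cut-off is E = 0.674, where the normal density is 0.3178. Then:

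- mean E in QL = −0.3178f/(1 − 0.25f)
- mean E in infiltration = +0.3178f/(1 + 0.25f)
- bias in outcome SDs = r × 0.6356f/(1 − 0.0625f²)
- expected QL count among 40 = 20(1 − 0.25f)

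For f = 0.5 and r = 0.5: 0.5 × 0.3178/0.984 = 0.16. For f = 1 and r = 0.5: 0.5 × 0.6356/0.9375 = 0.34, with an expected split of 15:25.

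Type I error comes from simulation (20,000 null trials per setting, two-sided Mann-Whitney; 4.7–4.8% with no redirection and free arm sizes). Ranges run from r = 0.3 to r = 0.5.

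| f | Bias (SD) | Type I error, 40 patients, arm sizes free | Type I error, arms filled to 20:20 |
|---|---|---|---|
| 10% | 0.02–0.03 | 5% | 5% |
| 25% | 0.05–0.08 | 5% | 5–6% |
| 50% | 0.10–0.16 | 6–7% | 6–8% |
| 100% | 0.20–0.34 | 8–16% | 9–18% |

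Against the planned effect of 1.0 SD, the 50% row is at most about a sixth and the 100% row at most about a third. On the plan's scale these are 0.16 × 2 = 0.32 and 0.34 × 2 = 0.68, against a difference of 2.

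**3. A different mechanism.** Suppose instead that an unwelcome draw is repeated once in 10%, 25% or 50% of cases, with the same r. The bias is about 0.03–0.04, 0.06–0.10 or 0.12–0.20 SD, and the type I error (t-test) about 5%, 5–6% or 7–9%. The message is the same: negligible if rare, material if frequent.

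**4. Unequal arms.** If each patient were a simple coin flip, the chance of 24:16 or worse among 40 is 2 × P(X ≤ 16) = 0.268, with X binomial(40, 0.5). At an effect of 1 SD, t-test power falls only from 0.869 (20:20) to 0.855 (24:16). This is minor.

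**The case against.** The strongest reply is that all of this rests on silence. A reader might infer that no locked sequence exists, or that the consenting investigators make the draws. The documents say neither: a full list may be generated once and held by someone else. That stands, so the point is that protection is not described, not that it is absent.

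A reader might also infer that bias would favour the QL block, because the protocol expects the block to be superior. The documents do not support a direction. Clinicians who believe in the block could as easily steer high-need donors towards it, which would count against QL. The protocol also acknowledges that the study may show no benefit of the block.

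The size is open to challenge too. A type I error of 15–18% requires every top-quarter donor drawn to QL to be redirected, with r = 0.5. That is systematic subversion, and with 40 patients it would leave a visible split of about 15:25. The correlation has no source in the documents. The exclusions for chronic pain, chronic opioid use, substance abuse and psychiatric disorder reduce what an investigator could use to predict need. These objections limit the magnitude.

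They do not supply the missing safeguard. A sound procedure that is not written down cannot be relied on or checked, and the tool as named does not provide one.

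**Conclusion.** The concern holds as a gap in the stated method. The protocol names a web randomizer and describes no locked list, concealment, release rule or audit trail, while investigators screen, consent and apply opinion-based exclusions in a trial with no described blinding. It is a risk left open and not evidence of bias.

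Under the assumed redirection mechanism with r = 0.3–0.5, redirection of 10–50% gives a bias of about 0.02–0.16 SD and a type I error of about 5–8%. Only complete redirection reaches about 0.20–0.34 SD and roughly 9–17%, the exact figure depending on whether the arms are held equal. How often steering would happen, and in which direction, cannot be known from the documents. The possible unequal split does not matter materially. The change is worth making because it is cheap and the harm could not be repaired afterwards.

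**What to change.** In Design & Procedures, replace the sentence naming the online randomizer with:

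> The department statisticians generate the 1:1 list once, in permuted blocks of varying size, and hold it in a locked REDCap randomization module (or, if unavailable, sequentially numbered opaque sealed envelopes). Each assignment is released, with a time stamp, only after consent and all eligibility criteria are recorded, and no assignment is redrawn.

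This closes both routes: the list cannot be foreseen by those who enrol, and a draw cannot be repeated. It also keeps the arms close to the equal split that the protocol states, wherever enrolment stops. Varying blocks are one acceptable method among several; the essential parts are independent custody, release after eligibility, and a record.

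The cost is a small amount of set-up work, and it gives REDCap and the statisticians an allocation role in addition to data storage and analysis. The 40 evaluable and 50 enrolled are unchanged, and clinical care is not affected. It must be in place before the first assignment it is meant to protect.
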